Our main end-points in the proposed studies are the synthesis rates of mixed-muscle protein, mixed-mitochondrial protein, as well as MHC isoforms, particularly MHC-I, whose synthesis rate we found to be lower in subjects with obesity, in our preliminary studies. These preliminary data also show that MHC-I synthesis rate does not increase in response to our experimental manipulation (i.e., exercise stimulus alone) despite an increase in MHC-I mRNA. Therefore, other main end-points are the expression of mRNA of MHC isoforms as well as the formation of the active eIF4F complex, which has key role in translation initiation in skeletal muscle, and which we found in our preliminary studies to be lower in muscle from humans with obesity. Statistical significance will be calculated using 2-way repeated measures ANOVA.

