We will study equal number of males and females. We have detected a difference of 1.1 SD with respect to eIF4F complex formation in the Basal state between subjects with obesity and lean controls. Therefore, a sample of 17 subjects with obesity and 17 lean subjects will have sufficient power (80%) to detect 1.1 SD difference ($\alpha = 0.05$) in eIF4F complex formation, and also will have >95% power ($\alpha = 0.05$) to detect a difference of 2.0 SD and 3.5 SD with respect to the rates of mixed-muscle protein synthesis and breakdown, respectively. Also, in the Basal state, we have detected a difference of 2.9 SD for MHC-I synthesis between groups, suggesting that 17 subjects/group will have >95% power to detect this difference ($\alpha = 0.05$). With respect to mRNA responses in the Basal state, we have detected a difference of 1.26 SD for MHC-IIx expression suggesting that a sample of 17 subjects/group will have >80% power to detect significant difference in this variable between groups ($\alpha = 0.05$). We have reported a difference of 2.3 SD in increasing mixed-muscle protein synthesis with increased plasma amino acid concentrations alone in humans with obesity (8). Considering a conservative estimate of a difference of at least half of that (i.e., 1.15 SD) in the response of the MHC-I, 17 subjects/group will provide >90% power ($\alpha = 0.05$) to detect statistically significant increase from Basal in the rate of synthesis of MHC-I in response to the increase in plasma amino acid concentrations coupled to the exercise stimulus in the subjects with obesity ($\alpha = 0.05$). We will test another 17 subjects with obesity that will serve as controls (i.e., increase in plasma amino acid concentrations alone), for a total of 34 subjects with obesity participating in the study. The same experiments will be performed in lean subjects, and where 17 subjects will undergo increase in plasma amino acid

Date: February 23, 2024

Protocol V11

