concentrations coupled to the exercise stimulus, and another 17 will serve as controls, for a total 34 lean subjects participating in the study. Main outcome in the exercise-alone studies is the increase in MHC-I mRNA expression after aerobic exercise, and which we show to increase only in the subjects with obesity. In our preliminary studies we detected a difference of 0.94 SD for MHC-I mRNA expression between before and after exercise in subjects with obesity. A sample of 9 subjects per group will have sufficient power (80%) to detect 0.94 SD difference ($\alpha = 0.05$) in MHC-I mRNA expression. Therefore, we will study 9 lean subjects and 9 subjects with obesity in the groups that will undergo exercise-alone trial. Sample size estimates and power were calculated using paired t-tests with an overall $\alpha = 0.05$ and $\alpha = 0.0125$ for Bonferroni-adjusted multiple comparisons. We propose to enroll 2 more subjects/group for the amino acid infusion and exercise+amino acid infusion studies (to the overall 34 subjects per group indicated above for those studies), to account for unsuccessful experiments and/or increase the statistical power in pair-wise comparisons with the lowest effect size, for a total of 36 lean subjects and 36 subjects with obesity for the studies related to the amino acid infusion and exercise+amino acid infusion. Therefore, we will enroll a total of 90 subjects.

Protection of Human Subjects

Risks to Human Subjects

Human Subjects Involvement, Characteristics, and Design

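### The power section names only paired t-tests, although its sizing contrast compares independent lean and obese groups, and the stated 80% for eIF4F does not reproduce as described

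*Combined protocol and SAP*

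**What the plan says.** All of this is in the section Statistical Design and Power.

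- **Test and alpha.** "Sample size estimates and power were calculated using paired t-tests", "with an overall $\alpha = 0.05$ and $\alpha = 0.0125$ for Bonferroni-adjusted multiple comparisons". No other test is named for sizing. The four comparisons implied by 0.0125 = 0.05/4 are not listed, and sidedness is not stated.
- **Sizing contrast.** "We have detected a difference of 1.1 SD with respect to eIF4F complex formation in the Basal state between subjects with obesity and lean controls". From this the plan concludes that "a sample of 17 subjects with obesity and 17 lean subjects will have sufficient power (80%) to detect 1.1 SD difference", with alpha printed as 0.05.
- **Other lean against obese contrasts in the Basal state, also at 17 per group.** Mixed-muscle synthesis (2.0 SD), mixed-muscle breakdown (3.5 SD), MHC-I synthesis (2.9 SD) and MHC-IIx mRNA (1.26 SD).
- **Within-subject contrasts.** Power above 90% "to detect statistically significant increase from Basal in the rate of synthesis of MHC-I" (1.15 SD, 17 subjects), and 80% for the before/after-exercise change in MHC-I mRNA in the exercise-alone groups (0.94 SD, 9 subjects).

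Every power figure is quoted at alpha 0.05; none is labelled 0.0125. The planned analysis is a two-way repeated measures ANOVA.

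**The concern.** A paired t-test needs two measurements on the same person or on matched persons. The plan describes no matching of lean to obese subjects, so the Basal eIF4F, MHC-I synthesis, mixed-muscle synthesis and breakdown, and MHC-IIx mRNA contrasts call for an independent-samples test. The paired test fits only the change from Basal and the before/after-exercise change.

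The second difficulty is the threshold. A reader sees 0.05 beside every figure and then a 0.0125 level with no statement of where it applies. As written, nobody can tell which test, at which alpha, on how many sides, produced the number that set the group size, or which threshold will decide significance.

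**Working it through.** **Inputs.** All come from Statistical Design and Power: d = 1.1, 1.15, 1.26 and 0.94 SD; n = 17 per group or 9; alpha 0.05 and 0.0125; 34 lean and 34 obese subjects across the amino-acid and exercise-plus-amino-acid trials. Sidedness is not given, so I take two-sided as the base case and show one-sided as the range.

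**Formulas.** Power is the probability that a noncentral t variable falls beyond the critical value.

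- Two-sample: df = 2n − 2, noncentrality = d × √(n/2).
- Paired: df = n − 1, noncentrality = d × √n, with d in SDs of the within-pair difference.

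**1. The plan's own figure (eIF4F, 1.1 SD, 17 per group, stated 80% at 0.05).**

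Two-sample noncentrality: 1.1 × √8.5 = 3.207, df = 32. Paired noncentrality: 1.1 × √17 = 4.535, df = 16.

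| Test | Alpha | Critical t | Power |
|---|---|---|---|
| Paired | two-sided 0.05 | 2.120 | 98.9% |
| Paired | two-sided 0.0125 | 2.813 | 94.3% |
| Two-sample | one-sided 0.05 | 1.694 | 93.2% |
| Two-sample | two-sided 0.05 | 2.037 | 87.5% |
| Two-sample | two-sided 0.025 = one-sided 0.0125 | 2.352 | 79.9% |
| Two-sample | two-sided 0.0125 | 2.647 | 71.0% |

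The plan does not say which SD the 1.1 is measured in. If it is the between-person SD and the notional pairs are uncorrelated, the paired noncentrality falls to 3.207 on 16 df, and power at two-sided 0.05 is 85.3%. So the paired test gives 85.3% to 98.9%, and on neither reading 80%.

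**2. What 0.0125 would do to the Basal contrast.** At two-sided 0.0125, 80% power needs 21 per group (20 gives 79.9%, 21 gives 82.3%). But the Experiments section gives every subject a Basal period before the experimental part, so the Basal comparison can draw on at least 34 per group: noncentrality 1.1 × √17 = 4.535, df = 66, critical t 2.568, power **97.3%**. With the 36 per group to be enrolled it is 98.1%.

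**3. The other figures at two-sided 0.0125.**

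- MHC-IIx mRNA, 1.26 SD, 17 per group, two-sample: 84.0% (stated above 80%; holds).
- Mixed-muscle synthesis, 2.0 SD, 17 per group, two-sample: 99.9% (stated above 95%; holds). The 2.9 and 3.5 SD contrasts are larger still.
- MHC-I synthesis, change from Basal, 1.15 SD, n = 17, paired: 96.1% (stated above 90%; holds). At two-sided 0.05 it is 99.4%.

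**4. Exercise-alone groups, where the paired test is right (0.94 SD, n = 9, stated 80% at 0.05).** Noncentrality 0.94 × √9 = 2.82, df = 8.

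- Two-sided 0.05: critical t 2.306, power **69.6%**.
- One-sided 0.05: critical t 1.860, power 82.3%.
- Normal approximation, two-sided 0.05: 80.5%.
- Two-sided 0.0125: critical t 3.206, power 41.5%.

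At two-sided 0.05, 11 subjects are needed for 80% (10 gives 75.4%, 11 gives 80.2%).

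**The case against.** The strongest reply is that this is one over-general sentence, not a sizing error. Much of that stands.

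- **Pairing did not inflate the eIF4F figure.** A reader might infer that it did. The paired test gives more than 80%, so the 80% was evidently obtained some other way. The sentence is also correct for the two within-subject contrasts.
- **The 80% may be a floor.** At the printed alpha a two-sided two-sample test gives 87.5%, so 17 per group is adequate there. That is fair, but a floor still does not reveal the test or alpha used.
- **The 71% is conditional.** A reader might infer that the trial misses its stated power at its own adjusted threshold. The documents do not support this. They print 0.05 beside the eIF4F contrast, attach 0.0125 only to unspecified comparisons, and never state sidedness. At one-sided 0.0125 the answer is 79.9%, so 17 per group may already reflect the Bonferroni level with the alpha mislabelled. And 34 per group will have Basal data.
- **Family-wise error.** A reader might count nine main end-points (two mixed-protein synthesis rates, three MHC synthesis rates, three MHC mRNAs, eIF4F) and compute 1 − 0.95⁹ = 37%, or 1 − 0.9875⁹ = 10.7%. Both assume independence, whereas the Specific Aims treat mRNA and eIF4F as drivers of synthesis. They also assume that the Bonferroni family runs across end-points; four pairwise contrasts within an end-point fit the text at least as well. These are not the trial's error rates.

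None of this answers the exercise-alone figure, which falls short with the test the plan names and the alpha it prints, unless the test was one-sided or a normal approximation was used. Neither is stated.

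**Conclusion.** The point holds as a defect in how the power calculations are specified. The named test is wrong for every lean against obese contrast, and the sizing figure does not follow from what is written: 98.9% with the named test (85.3% on the least favourable reading of the SD considered) and 87.5% with the appropriate one, against 80% stated. The use of 0.0125 is undefined.

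No Basal shortfall is shown. The 71% needs two-sided testing, 0.0125 applied to Basal eIF4F and only 17 per group; with 34 per group the figure is 97.3%.

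The one stated power that is materially too high is the exercise-alone figure: 69.6% against 80%, assuming a two-sided exact t-test at 0.05. If the test was one-sided, 82.3% supports the claim, but the plan would have to say so.

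**What to change.** Rewrite the power paragraph as follows.

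1. State a two-sample t-test for lean against obese contrasts and a paired t-test only for within-subject change.
2. Give test, sidedness, alpha and n beside each figure. For eIF4F at 17 per group: 87.5% at two-sided 0.05, or 71% at two-sided 0.0125.
3. Base the Basal lean against obese contrasts on everyone with the Basal measurement, at least 34 per group (eIF4F: 97.3% at two-sided 0.0125). Mixed-muscle breakdown is measured only in a subset according to the Experiments section, so state that number separately.
4. List the four comparisons that carry 0.0125, and say whether they lie within an end-point or across end-points.
5. Correct the exercise-alone figure to 69.6% at n = 9 (two-sided 0.05), or declare and justify a one-sided test, or plan 11 per group.

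An option, not a requirement: name MHC-I synthesis, which the plan already singles out, as the single primary end-point, with Holm across the rest.

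The cost is wording, plus some less favourable power figures. Only the choice of 11 per group would add subjects: 2 in each exercise-alone group, 4 in all.

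### Exercise-alone power is stated as 80% at n=9, but a two-sided paired t-test gives 69.6%; these groups have no reserve, and all four spares go to arms that already exceed 80% at alpha 0.05

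*Combined protocol and SAP*

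**What the plan says.** All of this is in the protocol's section Statistical Design and Power.

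- **Exercise-alone trial.** The main outcome is the rise in MHC-I mRNA after exercise. The effect comes from preliminary work: "we detected a difference of 0.94 SD for MHC-I mRNA expression between before and after exercise in subjects with obesity". The sample size follows from it: "A sample of 9 subjects per group will have sufficient power (80%) to detect 0.94 SD difference", at alpha 0.05. The plan therefore takes 9 lean and 9 obese subjects, with no additions.
- **AA and EX+AA trials.** The smallest effect powered here is the basal lean-versus-obese difference in eIF4F formation: "a sample of 17 subjects with obesity and 17 lean subjects will have sufficient power (80%) to detect 1.1 SD difference". The next is a 1.15 SD rise from Basal in MHC-I synthesis. The base is 17 per arm, or 34 per BMI group.
- **Spares.** "We propose to enroll 2 more subjects/group for the amino acid infusion and exercise+amino acid infusion studies", added "to the overall 34 subjects per group indicated above for those studies". The reason given is "to account for unsuccessful experiments and/or increase the statistical power in pair-wise comparisons with the lowest effect size". The result is stated as "for a total of 36 lean subjects and 36 subjects with obesity for the studies related to the amino acid infusion and exercise+amino acid infusion". The section ends: "Therefore, we will enroll a total of 90 subjects".
- **Method.** Power is said to come from paired t-tests, with an overall alpha of 0.05 and 0.0125 for Bonferroni-adjusted comparisons. The plan does not say whether the tests are one- or two-sided, or which comparisons take 0.0125.

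**The concern.** The exercise-alone outcome has the smallest effect in the section (0.94 SD) and the smallest groups (9). Nine subjects is few enough for the difference between a t-test and a normal approximation to matter, so the 80% needs checking against the named test. These groups also have no allowance for loss. Under Experiments, the exercise-alone trial follows the EX+AA procedures without the amino acids. Under Subject Monitoring, a subject whose exercise is discontinued leaves the infusion study. The exercise-alone groups are therefore exposed to that kind of failure too.

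What is at stake is a premise of Aim 2: that exercise raises MHC-I mRNA in subjects with obesity without raising MHC-I synthesis. If the mRNA rise is missed for lack of power, the argument for resistance at the translation step loses its first half.

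**Working it through.** **Inputs** (Statistical Design and Power): 0.94 SD, n=9, paired; 1.1 SD, 17 v 17, two independent groups; 1.15 SD, 17, paired; alpha 0.05 and 0.0125; four spares; total 90. Assumptions: tests are two-sided unless stated otherwise, and 0.94 is in SDs of the within-subject change, as a paired test implies.

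**1. Enrolment.** (34+2)×2 + 9×2 = 72 + 18 = 90, as stated. Spares: (36−34)×2 = 4, or one per arm (17 to 18).

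**2. Reproducing the stated 80%.** Normal approximation: Φ(d√n − 1.96) = Φ(0.94×√9 − 1.96) = Φ(0.86) = 80.5%. The stated figure is recovered this way.

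**3. The named test.** Power of a paired t-test is P(|T| > t_crit), where T is noncentral t with n−1 degrees of freedom and noncentrality d√n. At n=9 the noncentrality is 0.94×3 = 2.82 and t_crit(8 df) is 2.306, against 1.96 for the normal. Results for 0.94 SD:

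| n | two-sided 0.05 | one-sided 0.05 | normal, two-sided 0.05 | two-sided 0.0125 |
|---|---|---|---|---|
| 8 | 62.8% | 77.2% | 75.8% | – |
| 9 | 69.6% | 82.3% | 80.5% | 41.5% |
| 10 | 75.4% | 86.3% | – | 48.6% |
| 11 | 80.2% | 89.5% | 87.7% | 55.4% |

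Under the two-sided t-test at 0.05, n=11 is the first size to reach 80%. One lost subject takes every convention at 0.05 below 80%.

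**4. The arms that get the spares.** For two groups of n, the noncentrality is d√(n/2) with 2n−2 degrees of freedom. At 17 per group it is 1.1×√8.5 = 3.207. Results for 1.1 SD, two-sided:

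| n per group | alpha 0.05 | alpha 0.0125 |
|---|---|---|
| 14 | 80.0% | – |
| 16 | 85.3% | 67.4% |
| 17 | 87.5% | 71.0% |
| 18 | 89.4% | 74.2% |

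For the paired 1.15 SD response the noncentrality at 17 is 1.15×√17 = 4.74. Power is 99.0% at n=16, 99.3% at 17 and 99.6% at 18 (alpha 0.05).

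**5. What the spares buy.**
- Where they are: 1.1 SD gains 89.4 − 87.5 = 1.9 points at alpha 0.05, and 74.2 − 71.0 = 3.2 at 0.0125.
- In exercise-alone (9 to 11 per group): 0.94 SD gains 80.2 − 69.6 = 10.6 points at 0.05, and 55.4 − 41.5 = 13.9 at 0.0125.

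The 0.94 SD effect is a within-subject change in subjects with obesity, so only the two obese spares produce that gain. The two lean spares keep the groups balanced. A lean-versus-obese difference in change, if it were also 0.94 SD (an effect the plan does not give), would move only from 46.6% at 9 v 9 to 55.5% at 11 v 11.

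**The case against.** A reader might infer that the plan contradicts itself: spares meant for the lowest effect size are kept from the comparison with the lowest effect. The documents do not support this. The sentence is limited, at both its start and its end, to the AA and EX+AA studies, so the phrase can naturally mean the lowest effect within them, 1.1 SD. It also gives a second purpose, failed experiments. Those arms hold 68 of the 86 base subjects, so placing replacements there is coherent. This part of the objection stands in full.

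Three further arguments have weight.

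- **The 80% is not wrong under every convention.** Sidedness is not stated; a one-sided paired t-test gives 82.3%, and a two-sided normal approximation 80.5%. This stands as a condition on the finding. But the plan names t-tests, and a one-sided choice would have to be declared.
- **At alpha 0.0125 the AA and EX+AA arms are not comfortable either.** Power for 1.1 SD is 71.0% at 17 and 67.4% at 16, and exercise-alone reaches only 55.4% at n=11. This stands, and limits what moving the spares can promise. The gain is still larger in exercise-alone at that alpha.
- **Weighting reserves to the core arms is a legitimate preference.** The amino acid and combined trials carry the main Aim 2 hypothesis, while exercise-alone expands preliminary evidence. Arms of 18 can also be split evenly by sex; 17 and 11 cannot. This stands as a reason that the plan could give, but does not.

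**Conclusion.** The point holds in a limited form. With a two-sided paired t-test at alpha 0.05, the exercise-alone main outcome has 69.6% power at n=9, about 10 points below the stated 80%, and 62.8% after one failure. It has no reserve. The four spares go to studies that at alpha 0.05 already exceed the stated 80% for 1.1 SD, and that would still have 80.0% (rounded) at 14 per arm. This is an inefficient allocation of a fixed 90, not a breach of the plan's own wording.

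The size rests on two-sided testing at 0.05 and on 0.94 being in SDs of the paired change. If it is instead in SDs of the mRNA level, the paired effect is 0.94/√(2(1−r)), where r is the before–after correlation. That equals 0.94 at r = 0.5, is larger above it and smaller below it. The plan does not give r.

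It would also be too strong to say that all four spares would lift the main outcome to 80%: the two obese spares do that, and only if no experiment fails.

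**What to change.** Either of two changes would do.

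1. **Correct the statement.** Give exercise-alone power as about 70% at n=9 (two-sided paired t-test, alpha 0.05), state the sidedness for every power figure, and say which comparisons take 0.0125. Say also which comparison the spares are meant to strengthen and why the exercise-alone groups get none. This costs wording only.
2. **Move the spares within the total of 90.** Use 17 per arm in AA and EX+AA and 11 lean plus 11 obese in exercise-alone (34+34+11+11 = 90), and state 80% at n=11, with the sidedness and alpha. This changes wording and recruitment targets and adds no subjects.

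The second option has costs that the plan should acknowledge. AA and EX+AA lose their one spare per arm: with one failure per arm (n=16), power for 1.1 SD is 85.3% at alpha 0.05 and 67.4% at 0.0125. Exercise-alone holds 80% only if all 11 experiments in subjects with obesity succeed (75.4% at n=10), and reaches only 55.4% at alpha 0.0125. Arms of 17 and 11 cannot be split equally by sex.
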